## **11.4 Expectedness assessment**

All serious adverse reactions (serious adverse events assessed as possible, probable or definitely related to ChAdOx2CCHF administration) will be assessed for expectedness by the investigator. Expectedness will be determined according to the information set out in the reference safety section of the ChAdOx2 CCHF IB. As no expected SARs are recorded in the reference safety section of the ChAdOx2 CCHF IB, any SARs associated with ChAdOx2 CCHF will be classified as unexpected and reported as SUSARs in this trial.

## **11.5** Severity assessment

The severity of clinical and laboratory adverse events will be assessed according to scales based on FDA toxicity grading scales for healthy volunteers enrolled in preventive vaccine clinical trials. Severity scales for clinical and laboratory adverse events are shown in Appendix E.

REC Ref: <rec ref=""> IRAS project ID: 1007128 Protocol V2.0, 14th June 2023</rec>	CCHF01: A study of a new vaccine against Crimean-Congo Haemorrhagic Fever (a life- threatening tick-borne viral disease)	Page 49 of 78
---	--	---------------

## 11.6 Procedures for collecting and recording Adverse Events

Abnormal clinical findings from medical history, examination or blood tests will be assessed by a delegated clinician / Investigator to determine clinical significance.

All AEs that are observed by the Investigator or reported by the participant, irrespective of their relatedness to the study vaccination, will be recorded from the day of vaccination and until 28 days after each vaccination. These will be either recorded by the participants in the e-diary and/or in the eCRF. Outside of this window (i.e. from 28 days after each vaccination and until the point of a subsequent vaccination or until the final visit if vaccination course completed), non-serious AEs will only be recorded if they require medical attention (contact with GP, visit to emergency department). These will be recorded in the eCRF by the study team.

Type of AE	Study period	eDiary	eCRF
Solicited	Day 0-7	х	
Unsolicited	Day 0-7	х	х
	Day 8-28 post each vaccine dose	х	х
Chonened	Day 28-end of study (medically attended AEs only)		х

**Table 9:** Recording of solicited and unsolicited adverse events

## **11.7** Solicited Adverse Events

Predefined local and systemic solicited AEs for reactogenicity assessment, as listed in Table 9, will be collected in an electronic diary for 7 days following administration of the vaccine (see table x). Participants will measure and record their temperature and the diameter of any injection site redness or swelling with a provided thermometer and tape measure, and AE severity gradings will be calculated based on these measurements. For all other solicited AEs, solicited AE severity will be self-assessed by participants according to severity grading scales provided to them in the diary. Any solicited AE which meets the definition of a SAE will be managed and reported as per Section 11.5.

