## 5.9.1 Risks related to ChAdOx2 CCHF

The most likely side effects that recipients of ChAdOx2 CCHF may experience are short-lived local (primarily injection site tenderness or pain) and systemic vaccine reactions (fatigue, headache, malaise, feverishness) that resolve completely within days.

There has been a far wider clinical experience with ChAdOx1- than with ChAdOx2-vectored vaccines, particularly with ChAdOx1 nCoV-19 (Oxford/AstraZeneca COVID-19 vaccine). As noted above in Section 5.7, because of the close similarity between these two platforms, it may be anticipated that ChAdOx1- and ChAdOx2-vectored vaccines are likely to share similar safety profiles.

The frequency of the commonest adverse reactions to ChAdOx1 nCoV-19 are shown in Table 6 below.

Adverse Reaction	Frequency (%)
Injection site tenderness	68%
Injection site pain	58%
Fatigue	53%
Headache	53%
Malaise	44%
Myalgia	44%
Feverishness	34%
Arthralgia	27%
Nausea	22%
Fever over ≥38°C	8%

Table 6: Frequency of commonest adverse reactions to ChAdOx1 nCoV-19

Rarer adverse reactions associated with ChAdOx1 nCoV-19 are shown in Table 8, Section 11.2.

Post-marketing experience with ChAdOx1 nCoV-19 has revealed a very rare but serious side effect following vaccination with ChAdOx1 nCoV-19 (which has also been associated with the adenovirus-vectored Johnson & Johnson COVID-19 vaccine). This is known as thrombosis with thrombocytopenia syndrome (TTS) or vaccine-induced immune thrombotic thrombocytopaenia (VITT). It can present with venous thrombosis, often at unusual sites, such as cerebral venous sinus thrombosis (CVST) and splanchnic vein thrombosis. The condition can also present with arterial thrombosis.. It can lead to death or serious long-term disability.

There has been marked geographical variation in the reporting rates of TTS/VITT. The WHO Strategic Advisory Group of Experts (SAGE) noted reporting rates have been far lower outside of the UK and EU, despite the widespread use of the vaccine in many countries outside of Europe. An analysis of the AstraZeneca global safety database has shown reporting rates (in the 21 days after vaccination) vary, with 17.6 cases per million doses in Nordic countries, 10.0 cases per million doses in the UK and 0.2 cases per million doses in Brazil, South Korea and the Philippines.

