# 6 OBJECTIVES AND ENDPOINTS

# 6.1 Objectives, outcome measures and evaluation timepoints

Outcome	Objective	Outcome measure	Evaluation timepoints 
Primary	To assess the safety and tolerability of ChAdOx2 CCHF in healthy volunteers	
 
a) Occurrence of solicited local reactogenicity signs and symptoms
 
b) Occurrence of solicited systemic reactogenicity signs and symptoms
 
c) Occurrence of unsolicited adverse events (AEs)
 
d) Occurrence of abnormal safety laboratory measures
 
e) Occurrence of serious adverse events (SAEs) and adverse events
 
	7 days following each vaccination (D0 to D7; V2 to V2+7) 7 days following each vaccination
Secondary		of special interest (AESIs) Anti-CCHF glycoprotein specific serological response	Cohort 1 : D0, D28, V2, V2+28 Cohort 2 : D0, D28, V2, V2+28
	To compare the	Anti-CCHF glycoprotein specific serological response	Cohort 1 : D0, D28, V2, V2+28 Cohort 2 : D0, D28, V2, V2+28
Exploratory 	immunogenicity of ChAdOx2 CCHF vaccine in	a) Anti-CCHF glycoprotein specific serological response	Cohort 1 : D14, D56, V2+14, V2+56, V2+140, V2+280 Cohort 2 : D1, D14, V2+1, V2+14, V2+140, V2+280
		b) CCHF glycoprotein T cell response measured by IFN-γ ELISPOT	Cohort 1 : D0, D14, D28, D56, V2, V2+14, V2+28, V2+56, V2+140, V2+280 Cohort 2 : D0, D1, D14, D28, V2, V2+1, V2+14, V2+28, V2+140, V2+280
	-	a) Anti-CCHF glycoprotein specific serological response	Cohort 1 : D14, D56, V2+14, V2+56, V2+140, V2+280 Cohort 2 : D1, D14, V2+1, V2+14, V2+140, V2+280

individuals previously vaccinated with a ChAdOx vaccine with ChAdOx naïve individuals	b) CCHF glycoprotein T cell response measured by IFN-γ ELISPOT	Cohort 1 : D0, D14, D28, D56, V2, V2+14, V2+28, V2+56, V2+140, V2+280 Cohort 2 : D0, D1, D14, D28, V2, V2+1, V2+14, V2+28, V2+140, V2+280
Immunological profiling	
 
a) CCHF virus neutralising antibodies (using pseudoneutralization assays)
 
b) Cellular immune response to CCHF virus measured by ICS, proliferation and/or whole blood assays
 
c) Further immunological profiling
 
	Timepoints will be detailed in the laboratory analysis plan
To assess anti-vector immunity following vaccination	Binding and/or neutralising antibody responses against ChAdOx1	Timepoints will be detailed in the laboratory analysis plan

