REC Ref: <rec ref=""> IRAS project ID: 1007128 Protocol V2.0, 14th June 2023</rec>	CCHF01: A study of a new vaccine against Crimean-Congo Haemorrhagic Fever (a life- threatening tick-borne viral disease)	Page 47 of 78
---	--	---------------

Table 8 Adverse reactions to ChAdOx1 nCoV-19 vaccine (AZD1222)
--

MedDRA SOC	Term	Frequency*	Monitored AESI**
Blood and lymphatic	Lymphadenopathy	Uncommon	No
system disorders	Thrombocytopenia, Immune thrombocytopenia	Uncommon	Yes
Immune system disorders	Anaphylaxis, hypersensitivity	Uncommon	Yes
Metabolism and nutrition disorders	Decreased appetite	Uncommon	No
Nervous system	Headache	Very common	No
disorders	Dizziness, somnolence, lethargy	Uncommon	No
	Facial paralysis	Rare	Yes
	Guillain-Barré syndrome	Very rare	Yes
	Transverse myelitis	Not known	Yes
Vascular disorders	Thrombosis with thrombocytopenia syndrome	Very rare	Yes
	Cerebrovascular venous and sinus thrombosis	Not known	Yes
	Capillary leak syndrome	Not known	Yes
Gastrointestinal	Nausea	Very common	No
disorders	Vomiting, diarrhoea	Common	No
	Abdominal pain	Uncommon	No
Skin and subcutaneous tissue	Hyperhidrosis, pruritus, rash, urticaria	Uncommon	Yes (urticaria)
disorders	Angioedema	Not known	Yes
Musculoskeletal and	Myalgia, arthralgia	Very common	No
connective tissue	Pain in extremity	Common	No
disorders	Muscle spasms	Uncommon	Yes
General disorders and administration site conditions	Injection site tenderness, pain, warmth, pruritus, bruising, fatigue, malaise, feverishness, chills	Very common	No
	Injection site swelling, erythema, induration, pyrexia, influenza-like illness, asthenia	Common	No

\* very common ( $\geq$ 1/10); common ( $\geq$ 1/100 to <1/10); uncommon ( $\geq$ 1/1,000 to <1/100); rare ( $\geq$ 1/10,000 to <1/1000); very rare (<1/10,000) and not known (cannot be estimated)

\*\*AEs listed that are not AESIs will be captured as solicited and/or unsolicited AEs

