## Table 10 Solicited Adverse Events

Local solicited AEs	Systemic solicited AEs
Redness at the injection site (measured)	Fever (measured)
Warmth at the injection site	Chills
Itch at the injection site	Feverishness

Pain at the injection site	Joint pains
Swelling at the injection site	Muscle pains
	Fatigue
	Headache
	Nausea
	Malaise

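### Injection-site tenderness, the most frequent reaction in Table 6, is the only one of its ten reactions not solicited, so primary outcome (a) under-ascertains and misclassifies it

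*Protocol*

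**What the plan says.** Primary outcome (a) in Section 6.1 is "Occurrence of solicited local reactogenicity signs and symptoms", assessed over the 7 days after each vaccination. Section 11.7 describes what feeds it: "Predefined local and systemic solicited AEs for reactogenicity assessment", entered in the eDiary. The list is in Table 10 (Section 11.7 cites it as Table 9). Its local column holds redness, warmth, itch, swelling and "Pain at the injection site". Tenderness does not appear.

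Two other places in the protocol treat tenderness as an expected reaction distinct from pain:

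- Section 5.9.1 describes the likely local side effects of ChAdOx2 CCHF as "primarily injection site tenderness or pain". Table 6 then gives tenderness and pain separate rows, at 68% and 58%.
- The ChAdOx1 nCoV-19 reaction table in Section 11.2 (Table 8) has, in its very common category, "Injection site tenderness, pain, warmth, pruritus, bruising, fatigue, malaise, feverishness, chills".

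The footnote to that Table 8 says that listed reactions which are not AESIs will be recorded by the solicited route, the unsolicited route, or both. Section 11.8 says unsolicited events are gathered by open questions, and its example asks about new illnesses. Unsolicited events form primary outcome (c).

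**The concern.** The trial is open-label, has no control group and is descriptive (Sections 7 and 13.1.1). Its main product is a set of reactogenicity rates, and those rates depend on what the diary asks. A reaction with its own prompt each day is ascertained differently from one that a participant must think to mention. A sore-to-touch arm is not an obvious answer to a question about new illnesses.

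The omission also affects the item that is asked. The protocol separates tenderness from pain twice, and nothing says that the pain item includes tenderness. Some participants will enter tenderness as pain, some will volunteer it, and some will leave it out. The resulting pain rate is then neither clearly pain alone nor clearly pain or tenderness.

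This cannot be left to a statistical analysis plan, because no analysis can recover an answer to a question that was not put.

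**Working it through.** The protocol gives no sample-size or power calculation, so there is no figure of its own to reproduce. The check has two parts.

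**1. Table 6 against Table 10, row by row**

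| Table 6 reaction | Rate | Item in Table 10 |
|---|---|---|
| Injection-site tenderness | 68% | none |
| Injection-site pain | 58% | pain at the site |
| Fatigue | 53% | fatigue |
| Headache | 53% | headache |
| Malaise | 44% | malaise |
| Myalgia | 44% | muscle pains |
| Feverishness | 34% | feverishness |
| Arthralgia | 27% | joint pains |
| Nausea | 22% | nausea |
| Fever | 8% | fever (measured) |

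Nine of ten are solicited. The one left out is the most frequent. Table 10 also solicits redness and swelling, which Table 8 (as erythema and swelling) rates only as common, so low expected frequency does not explain the choice. Table 10 breaks across a page, but its local column ends in blank cells beside the remaining systemic items, so no local row appears to have been lost.

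**2. Size, if the Table 6 rates applied here**

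Inputs: P(T) = 0.68 for tenderness and P(P) = 0.58 for pain (Table 6), each read as a share of vaccinees; n = 46 (Section 13.1.2), with 20 in each Cohort 2 group.

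- Expected with tenderness: 46 × 0.68 = 31.3.
- Expected with pain: 46 × 0.58 = 26.7.
- The overlap of the two is not given, so tenderness without pain can only be bounded.
  - Lower bound: max(0, 0.68 − 0.58) = 0.10, and 46 × 0.10 = 4.6.
  - Upper bound: min(0.68, 1 − 0.58) = 0.42, and 46 × 0.42 = 19.3.
- In one Cohort 2 group: 20 × 0.10 = 2 to 20 × 0.42 = 8.4.
- Chance of at least one such participant among 46 at the lower bound: 1 − 0.90^46 = 0.992.

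**3. What these bounds do not show**

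Tenderness without pain is not the same as tenderness with no solicited local reaction. Warmth is also solicited, and Table 8 rates it at 1 in 10 or more. Allowing for warmth at just that threshold, the guaranteed minimum is 0.68 − 0.58 − 0.10 = 0, and itch, redness and swelling could only lower it further. The documents therefore give no positive minimum for participants who would be counted as having no local reaction at all.

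**The case against.** The strongest reply is that tenderness is not lost. Section 5.9.1 pairs it with pain as the typical local reaction, and pain is solicited, so the pain item will absorb some of it. Volunteered tenderness enters primary outcome (c). Unsolicited events are recorded in the same eDiary over days 0 to 28, with reminders for missed entries (Section 9.6) and review at clinic visits. The Table 8 footnote allows either route, so the protocol does not promise to solicit every listed reaction and does not contradict itself.

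All of this stands, and it limits the point to under-ascertainment and misclassification in outcome (a). It does not remove the point. The unsolicited route has no tenderness prompt, and absorption into pain is exactly what makes the pain rate hard to interpret.

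A second reply is that the 68% belongs to another vaccine. Section 5.9.1 anticipates that "ChAdOx1- and ChAdOx2-vectored vaccines are likely to share similar safety profiles", but Section 11.2 says it is not known whether the profiles will be similar. This also stands: every count above is conditional. The omission itself does not depend on the rate, because Section 5.9.1 names tenderness first as an expected reaction to this vaccine.

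A third reply is that no comparison with ChAdOx1 rates is planned, and that nine of the ten reactions could be set beside them anyway. That is fair. What is missing is one term, not the whole local profile.

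**Conclusion.** The point holds as a cheap improvement to the measurement of a primary safety outcome. Tenderness is the only Table 6 reaction without a solicited item, and it is the top one. Followed as written, the trial will have no solicited tenderness rate and a pain rate of uncertain meaning. If the Table 6 rates carried over and are shares of vaccinees, about 31 of 46 participants would have tenderness, about 27 pain, and 5 to 19 tenderness without pain. The last range is a bound, not an estimate.

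A reader might infer more, and the documents do not support it:

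- That the trial misses tenderness altogether. It can still enter through pain or through outcome (c).
- That at least 10% of participants would wrongly count as having no local reaction. The 10% bounds tenderness without pain only.
- That the safety holding rules are weakened. Section 11.21.1 covers solicited and unsolicited events, and its unsolicited criterion has no 2-day onset limit, so no weaker protection is shown.
- That bruising should be solicited on the same grounds. It is not in Table 6, and the only rate given is 1 in 10 or more.

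**What to change.** Add tenderness at the injection site to Table 10 and to the eDiary as an item separate from pain. Grade it on the existing Appendix E scale for any symptom, and report it in primary outcome (a). Make Section 5.9.1 with Table 6, Table 8 in Section 11.2, and Table 10 use the same terms.

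Stating that the pain item includes tenderness would be a lesser remedy. It would remove the ambiguity but would still give no separate tenderness rate.

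The cost is one more diary item on days 0 to 7 after each of the two doses, plus edits to the table and the diary. No new visit, staff or grading scale is needed.

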## Table 10 Solicited Adverse Events

Local solicited AEs	Systemic solicited AEs
Redness at the injection site (measured)	Fever (measured)
Warmth at the injection site	Chills
Itch at the injection site	Feverishness

Pain at the injection site	Joint pains
Swelling at the injection site	Muscle pains
	Fatigue
	Headache
	Nausea
	Malaise

## **11.8 Unsolicited Adverse Events**

Unsolicited adverse events, *i.e.* those collected through open questioning (*e.g.* "did you experience any new illnesses?"), that are not solicited adverse events and do not constitute SAEs or AESIs, will be collected from the day IMP is administered to the end of the study as follows:

- Day 0 day 28 post each vaccine: These will be recorded in the participant's eDiary and/or ecRF. All reported events will be reviewed at clinic visits and transferred to relevant eCRF on the clinical database if necessary.
- Day 28 to subsequent vaccination or until the final visit (if vaccination course completed) only non-serious medically attended AEs that occur from the time of vaccination to the end of the study will be recorded in the relevant eCRF on the clinical database.

Severity will be self-assessed by participants according to severity grading scales provided to them. Causality will be assigned by the PI-delegated clinician / Investigator as per section 11.3.

If clarification of any event is required, then the study nurse or doctor will seek this from the participant during a clinic visit or by telephone call.

## **11.9 Observation related AEs**

Physical observations of the patient (*e.g.*, temperature, blood pressure) will be taken at each visit. These will be recorded in the eCRF. If abnormal, a severity grading will be assigned as described in Appendix E.

## 11.10 Laboratory AEs

Severity grading for laboratory AEs is described in Appendix E. All changes in laboratory values will be recorded as AEs if they are of Grade 2 severity or above and will be entered into the relevant eCRF in the clinical database. Changes of laboratory values of Grade 1 severity may be recorded as AEs if they are judged to be clinically significant by a PI-delegated clinician / Investigator.

If a test is deemed clinically significant, it may be repeated to ensure it is not a single occurrence or spurious result. If a test remains clinically significant, the volunteer will be informed and advised about appropriate medical care. If abnormal laboratory values are the result of pathology for which there is an overall diagnosis, then this diagnosis will be reported as one AE only.

A Grade 4 laboratory AE will be considered a SAE.

REC Ref: <rec ref=""> IRAS project ID: 1007128 Protocol V2.0, 14th June 2023</rec>	CCHF01: A study of a new vaccine against Crimean-Congo Haemorrhagic Fever (a life- threatening tick-borne viral disease)	Page 51 of 78
---	--	---------------

## 11.11 Notes on recording AEs

Pre-existing medical conditions (present prior to enrolment into the study) are considered "concurrent medical conditions" and should not be recorded as AEs. However, if the participant experiences a worsening or complication of the condition, the worsening or complication should be recorded as an AE. Study staff will ensure that the AE term recorded captures the change in the condition (*e.g.*, "worsening of").

Each AE will be recorded to represent a single diagnosis. Accompanying signs or symptoms (including abnormal laboratory values) will not be recorded as additional AEs.

Any pregnancy occurring during the clinical study and the outcome of the pregnancy should be recorded and followed up for congenital abnormality or birth defect, in which case it would fall within the definition of "serious" and the congenital abnormality of birth defect would be reported as an SAE. Pregnancy notification and follow-up reports on pregnancy outcome will be provided to the DSMC with the ongoing consent of the participant.

## 11.12 Follow up of AEs

AEs considered related to the active vaccine will be followed until resolution, the event is considered stable or until non-study causality is assigned. At the end of the study all other ongoing/open AEs will be assessed by a PI-delegated clinician / Investigator, to ensure, if not already done so, that adequate medical follow-up (if required) has been arranged, *e.g.* referral to the participant's GP.

All AEs that result in a participant's withdrawal from the study will be, subject to participant consent, followed up where possible until a satisfactory resolution occurs, or until a non-study related causality is assigned. This will involve an end of study assessment at which the requirement for further appropriate care under medical supervision will be determined. If required, the participant will be referred to their GP for ongoing medical supervision, until symptoms cease, or the condition is deemed resolved or stable.

## **11.13** Reporting procedures for SAEs

SAEs will be collected throughout the entire trial period (from first vaccination to the final study visit or withdrawal).

All SAEs must be recorded on a SAE form (on REDCap, or paper backup) with causality assessed by the Investigator and reported by email to the CI. All SAEs will be reported to the DSMC Chair (or nominated designee) within 24 hours of discovery or notification of the event. If the PI deems that this is a SUSAR, this will be reported according to the SUSAR reporting procedures in section 11.14. In the absence of the PI these tasks may be performed by a Co-Investigator.

Additional information received for a case (follow-up or corrections to the original case) will be detailed on an electronic SAE form which is linked to the original report. An automated email alert will be sent to the CI, the lead study Dr, the Quality Assurance lead, the lead nurse, the project manager and the sponsor assessors.

The chair of the DSMC (or nominated designee) will perform an independent review of SAEs and request any further information required in a manner adherent to the procedures and timelines of

REC Ref: <rec ref=""> IRAS project ID: 1007128 Protocol V2.0, 14th June 2023</rec>	CCHF01: A study of a new vaccine against Crimean-Congo Haemorrhagic Fever (a life- threatening tick-borne viral disease)	Page 52 of 78
---	--	---------------

the DSMC Charter. Documentation of this review will be kept in the TMF. The DSMC will provide independent safety assessment throughout the study as per section 11.18.

